5.11 Treatment Restrictions

The following therapies may not be used before end of Day 28 of the study:

- Chemotherapeutic or agents with known anti-cancer activity for the disease under study
- Radiation therapy
- Immunotherapy
- Immunosuppressive agents including corticosteroids, except for low dose corticosteroids used for concomitant medical conditions.
- Any other investigational agent.

Topical or inhalational steroids are permitted. Investigators may prescribe concomitant supportive medications or treatments deemed necessary to provide adequate patient care.

All prescription and non-prescription concomitant medications must be recorded in the eCRF, listing generic name, indication, dose and schedule and dates of administration.

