	• Expected survival > 3 months			
	• 18 years or older			

Main Exclusion Criteria	 Undergoing treatment (chemotherapy, immunotherapy or radiation) within 4 weeks of entering this study or planned to receive treatment 		
	within 4 weeks of entering this study of planned to receive treatment within 4 weeks after receiving the study drug		
	Disease-specific criteria		
Study Analyses	Interim analysis after evaluation of the last patient in the second dose		
	level ends		
	Final analysis: at the end of the study		
Study Duration	12 -18 months		
Anticipated Study Start Date	Q1 2012		
Anticipated Enrolment	Q1 2013		
Completion			
Anticipated Study Completion	Q1 2013		

Figure 1. PROTOCOL SCHEMA

- If no patients entered in the 1st dose group experience a dose-limiting toxicity (DLT) (as defined in Section 3.1), then the next dose group may commence 30 days after the last patient on the previous dose group has received the ¹²⁴I-PEG-AVP0458 infusion.
- If any one patient in either cohort of 3 patients experiences a DLT, then 3 additional patients will be entered in that dose group.
- If additional patients are treated in the first dose group, all patients entered must have been observed for 30 days before a new patient may receive an infusion in the second dose group.
- In the event 2 or more patients experience DLT at the first dose level, an additional 3 patients will be entered at a 0.5mg/m² dose level
- Interim analysis will evaluate safety and imaging data available after the dose escalation part of the study and will determine which of the two doses be administered to the last 6 patients in the study. The dose selected will be based on imaging characteristics and pharmacokinetic data of ¹²⁴I-PEG-AVP0458 at each dose level.

TABLE OF CONTENTS

S1	TUDY	PERSONNEL	2
Pı	rotoco	ol Synopsis	6
T/	ABLE (OF CONTENTS	8
A	BBRE\	VIATIONS	12
		ULE OF EVENTS	
1		CKGROUND AND RATIONALE	
	1.1	Ovarian Cancer	
	1.2	Prostate Cancer	
	1.3	AVP0458	
	1.3.1		
	1.	.3.1.1 Expression of TAG-72 in prostate cancer	
	1.	.3.1.2 Expression of TAG-72 in ovarian cancer	18
	1.	.3.1.3 Clinical evaluation of anti-TAG-72 antibodies	18
	1.3.2	2 Antibody based cancer therapy and radioimmunodetection	18
	1.3.3	Recombinant Diabodies	19
	1.3.4	4 AVP0458 Drug Description	19
	1.3.5	Biodistribution of ¹²⁴ I-PEG-AVP0458 in LS174T Xenograft Model	20
	1.4	Rationale for the Study	20
2	STU	JDY OBJECTIVES	20
	2.1	Primary Objective	20
	2.2	Secondary Objectives	20
3	STU	JDY DESIGN	21
	3.1	Summary of Design	21

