There are several treatments available for localised prostate cancer and they include active surveillance (watchful waiting); surgery with a radical prostatectomy; radiation, including conformal external beam radiotherapy, brachytherapy with seeds and high dose rate brachytherapy; high intensity focused ultrasound; and hormone therapy, which is used to shrink the prostate and the tumour prior to radiotherapy. If the prostate cancer has already spread to other organs or to bone at the time of diagnosis, hormone therapy becomes the primary method of treatment. Most advanced prostate cancers respond well to hormone therapy and can do so for several years.

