4.2.1 Ovarian cancer

- Patients with relapsed or refractory ovarian cancer
- TAG-72-positive tumours (see Section 4.4)
- Detectable metastatic disease deemed likely to be assessable by PET by nuclear medicine physician as seen on imaging (see Section 4.5) performed within 21 days of enrolling in the study.
- ECOG Performance Status of 0-1 (Appendix 1)
- Expected survival of \geq 3 months
- 18 years of age or greater
- Platelet count ≥100 x 10⁹/L
- Absolute neutrophil count $\geq 1.5 \times 10^9/L$
- Aspartate Aminotransferase (AST) ≤3x upper limit of normal (ULN), or <5x ULN with liver metastases
- Total bilirubin ≤ 34 μmol/L
- Serum creatinine ≤160 µmol/L
- Provision of written informed consent.

Prostate cancer 4.2.2

- Patients with metastatic prostate cancer, or primary prostate cancer who are preprostatectomy or pre-radiotherapy
- TAG-72-positive tumours (see Section 4.4)
- Detectable disease deemed likely to be assessable by PET by nuclear medicine physician as seen on imaging (see Section 4.5) performed within 21 days of enrolling in the study
- ECOG Performance Status of 0 or 1 (Appendix 1).
- Expected survival of \geq 3 months
- 18 years of age or greater
- Platelet count ≥100 x 10⁹/L
- Absolute neutrophil count $\geq 1.5 \times 10^9/L$
- AST $\leq 3x$ ULN, or < 5x ULN with liver metastases
- Total bilirubin ≤ 34 μmol/L
- Serum creatinine ≤160 µmol/L
- Provision of written informed consent.

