4.3.2 Prostate cancer

- Chemotherapy (not including androgen deprivation therapy), immunotherapy, biologic therapy, radiation therapy, or other investigational product within 4 weeks prior to study entry or likely to be required during the 4-week on-study period
- Patients using corticosteroids or immunosuppressive agents: low dose oral corticosteroids for concomitant medical conditions are permitted. Inhaled or topical corticosteroids are permitted.
- Patients with active infections requiring antibiotics, with bleeding disorders or with other serious illness
- Patients with a concurrent active serious medical condition likely to affect participation in the study, such as a documented myocardial infarction ≤3 months prior or to screening or unstable angina pectoris
- Men who are unwilling to utilize a medically acceptable method of contraception
- Patients unable to sign informed consent or unwilling to comply with the procedural requirements of this clinical protocol.

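### Section 5.11 bars anti-cancer agents to Day 28 without the androgen-deprivation exemption in 4.3.2, so a man continuing that therapy is eligible under one rule and in breach of the other

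*Protocol*

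**What the plan says.** Two sections govern anti-cancer therapy during the study in men with prostate cancer.

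- **Section 4.3.2 (exclusion criteria).** The first criterion opens with "Chemotherapy (not including androgen deprivation therapy" (the bracket closes there) and goes on to other anti-cancer and investigational treatments. It applies both to the four weeks before entry and to treatment "likely to be required during the 4-week on-study period".
- **Section 5.11 (treatment restrictions).** The list of therapies not allowed before the end of Day 28 starts with "Chemotherapeutic or agents with known anti-cancer activity for the disease under study". The only exception inside the list is in the immunosuppressant bullet: "except for low dose corticosteroids used for concomitant medical conditions". Below the list, topical and inhaled steroids and supportive treatment are allowed. Androgen deprivation is not mentioned.

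Three other places bear on the reading. Section 1.2 says "Most advanced prostate cancers respond well to hormone therapy and can do so for several years", and among treatments for localised disease lists "hormone therapy, which is used to shrink the prostate and the tumour prior to radiotherapy". Section 4.2.2 admits men with metastatic disease and men with "primary prostate cancer who are preprostatectomy or pre-radiotherapy". The synopsis, under its main exclusion criteria, gives the barred treatment as "Undergoing treatment (chemotherapy, immunotherapy or radiation" and does not mention hormone therapy.

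**The concern.** The two sections cover the same four weeks after infusion and give opposite answers for a man whose androgen deprivation continues. Section 4.3.2 admits him knowingly. Section 5.11, as worded, forbids the treatment.

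A site that obeys 5.11 has to interrupt effective cancer therapy in a patient who is in the study for a single imaging dose. A site that follows 4.3.2 has an eligible patient in breach of the protocol, and Section 5.14 allows withdrawal for non-compliance. There are two participating sites, and nothing in the protocol makes them resolve the conflict in the same way.

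**Working it through.** The check is mainly textual; the only arithmetic is a count of the patients who could be affected.

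**The two rules compared**

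| | Section 4.3.2 | Section 5.11 |
|---|---|---|
| Period after infusion | 4-week on-study period | to the end of Day 28 |
| Scope | chemotherapy, immunotherapy, biologic therapy, radiation, other investigational product | chemotherapeutic agents or any agent active against the disease; radiation; immunotherapy; immunosuppressants; other investigational agents |
| Low-dose, topical and inhaled steroids | allowed | allowed |
| Androgen deprivation | exempt | no exemption |

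**Step 1: do the periods overlap?** Yes. The exemption in 4.3.2 sits in one sentence governing both the period before entry and the on-study period. It cannot be read as applying before entry only.

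**Step 2: does androgen deprivation fall within the wording of 5.11?** Yes. The bullet goes beyond chemotherapy to any agent with known activity against the disease. Section 1.2 describes hormone therapy as the main treatment once prostate cancer has spread, as effective for years in most advanced cases, and as a means of shrinking the tumour before radiotherapy. The permission for supportive treatment in 5.11 does not cover a disease-directed therapy.

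**Step 3: does anything reconcile the two?** No. Nowhere does the protocol carry the exemption into 5.11, tell men to stop androgen deprivation, or say which section prevails. Because 5.11 restates one set of exceptions from 4.3.2 and not the other, a monitor could reasonably take the omission as deliberate.

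**Step 4: how many patients?** Inputs are from Sections 3.1 and 3.2.

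- Dose group 3 fixes 3 prostate patients out of 6.
- The escalation part takes either tumour type: 0 to 6 prostate patients out of 6, or 0 to 12 out of 12 if both cohorts expand.
- Without expansion: 3 + 0 = 3 to 3 + 6 = 9 of 12.
- With full expansion: 3 + 0 = 3 to 3 + 12 = 15 of 18.
- The share continuing androgen deprivation after Day 0 is not stated. Assuming anything from 0% to 100%, the number affected is 0 to 9 of 12, or 0 to 15 of 18.

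**Step 5: does it reach the analysis?** Not directly. The safety population in Section 8.3 needs an infusion and one later safety assessment; the evaluable population needs four weeks of completed assessments; evaluability in Section 5.13 depends on completed procedures. None turns on prohibited medication.

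**The case against.** The strongest reply accepts the wording gap and disputes its consequence. The only sentence that names androgen deprivation is the one allowing it. An investigator faced with a specific exemption and a loosely drafted general bullet would probably follow the exemption or ask the sponsor. Withdrawal under 5.14 is optional and follows discussion between sponsor and investigator. The realistic outcome is a query or a logged deviation. That stands, and it limits the rating. It does not make 5.11 correct: the patient's treatment should not depend on an investigator choosing to disregard an operative restriction.

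The upper end of the range is also extreme. It needs every escalation patient to have prostate cancer and every one of those men to continue androgen deprivation; 15 of 18 also needs both cohorts to expand. Section 1.2 ties hormone therapy to metastatic disease and to use before radiotherapy, not to men awaiting prostatectomy. This is fair: the range bounds the number and does not estimate it.

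The synopsis is weak evidence of intent. It is abbreviated and also omits biologic therapy and investigational products, which 4.3.2 does exclude. The inference that androgen deprivation is meant to be allowed therefore rests mainly on 4.3.2.

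**Conclusion.** The contradiction is real and rests only on the protocol's own text. Androgen deprivation continued after Day 0 is allowed by 4.3.2 and prohibited by 5.11. The intent is most likely to allow it, so 5.11 is the section that is wrong as written.

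The size is minor to moderate. The harm is to patient management and to the reporting of deviations; endpoints, dose decisions and the primary safety analysis are unaffected. Only men whose therapy continues on study are concerned. Their number is not given and may be zero; the upper limits of 9 of 12 and 15 of 18 hold only under the assumption that all prostate patients are on such therapy. Because Section 1.2 describes hormone therapy in two of the groups that 4.2.2 admits, the case is foreseeable and should be settled in the text.

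**What to change.** Add to the first bullet of Section 5.11: *except ongoing androgen deprivation therapy in patients with prostate cancer*. This brings it into line with 4.3.2 and is consistent with the synopsis. If the sponsor does mean to bar the therapy, delete the exemption in 4.3.2 instead, so that men who need it are not enrolled.

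Optionally, list androgen-deprivation status beside the tumour uptake values of prostate patients. Section 1.3.1.1 gives a reason: one cited study found TAG-72 reactivity in 10 of 20 hormonally treated specimens (50%) against 21 of 25 untreated (84%), although a later study cited there found most prostate cancers strongly positive irrespective of grade, stage or pre-operative PSA. The contradiction is resolved without this listing.

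The cost is one clause in a protocol amendment. No new data are needed, because concomitant medications are already recorded at every visit.

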5.12 Concomitant Diagnosis and Therapies

In this trial, a pre-existing condition (i.e., a disorder present before the AE reporting period started) should not be reported as an AE unless the condition worsens during the AE reporting period.

Diagnostic and therapeutic non-invasive and invasive procedures, such as surgery, should not be reported as AEs. However, the medical condition for which the procedure was performed should be reported if it meets the definition of an AE. For example, an acute appendicitis that begins during the AE reporting period should be reported as the AE and the resulting appendectomy noted under Comments.

Concomitant supportive medications or therapy to provide adequate care may be prescribed as necessary and will be documented in the patient's medical history and eCRF. All prescription and non-prescription concomitant medications and treatments will be recorded at each visit in the eCRF. Trade or generic name, indication, quantity administered, route, and dates of administration will be listed. Treatment history will include the 4 weeks prior to the first infusion of ¹²⁴I-PEG-AVP0458.

SSKI (10 drops, twice daily) will be given immediately prior to the 124 I-PEG-AVP0458 infusion, continuing for a total of 10 days. The administration of this agent is to prevent the uptake of radioiodine in the thyroid gland.

5.13 Patient Evaluability

All patients who receive the infusion of ¹²⁴I-PEG-AVP0458 diabody will be evaluable for safety. Every effort will be made to obtain complete information on all AEs, with particular emphasis on serious AEs, infusional toxicities, and hypersensitivity reactions. Patients will be evaluable for biodistribution and pharmacokinetics assessment if they complete all study procedures up to Visit 4 (Day 6 or 7

visit). Patients will be evaluable for immunogenicity of PEG-AVP0458 if they have completed the Day 28 (±2 days) visit procedures.

5.14 Criteria and rules for stopping patient treatment

An Investigator may stop a patient's participation for the following reasons:

- The patient withdraws consent.
- The patient is no longer able to participate.
- A patient can be withdrawn after discussion between the Sponsor and Investigator if eligibility criteria are violated or if the patient fails to comply with the protocol (e.g., nonadherence to study assessment visits).
- The Investigator's judgment that continued participation is no longer in the patient's interest.

Documentation of the details of withdrawal will be included in the eCRF. All patients who receive the ¹²⁴I-PEG-AVP0458 infusion will be evaluated for safety.

5.15 Patient Replacement

Any patient who does not complete the scheduled visits (up to 4 weeks after receiving the therapeutic infusion) for reasons unrelated to study drug administration may be replaced.

6 Study assessments

6.1 Safety Evaluation

Safety of ¹²⁴I-PEG-AVP0458 will be determined by the ongoing monitoring of the incidence and intensity of AEs graded using the National Cancer Institute Common Terminology Criteria for Adverse Events (CTCAE) v4.0 (Appendix 2), with special emphasis on DLT events and infusional toxicities. A copy of CTCAE v4.0 also may be downloaded from the Cancer Therapy Evaluation Program home page (http:\\ctep.info.nih.gov).

A DLT is defined as any of the following events occurring within 30 days of study drug administration:

- Any Grade 2 or greater allergic reaction.
- Any Grade 3 toxicity. Exceptions are: fever; asymptomatic hyperglycemia; hypophosphatemia; nausea, vomiting, or diarrhoea despite the use of optimal supportive medical therapy; leukopenia or thrombocytopenia that revert to baseline within three weeks of occurrence; lymphopenia without other dose-limiting events (eg opportunistic infection).
- Any Grade 4 toxicity.

To be dose-limiting, a toxicity must be possibly, probably, or definitely related to the administration of ¹²⁴I-PEG-AVP0458. All DLTs must be discussed with the study Coordinating Principal Investigator.

AEs will be collected after the patient has been enrolled. AEs occurring after signing informed consent but prior to receiving study drug (ie before enrolment) should only be reportable if related to study procedures. All AEs occurring after enrolment must be recorded until 30 days following the end of treatment exposure. Refer to Section 7.2.1. AEs include adverse drug reactions, any unfavourable sign or symptom (related and unrelated), illnesses with onset during the study, or exacerbations of pre-existing illnesses or conditions. Progression of the patient's malignancy should not be considered an AE, unless, in the Investigator's opinion, study treatment resulted in an exacerbation of the patient's condition. Exceptions are if disease progression results in death or hospitalization while on study or within 30 days of the last dose. If either occurs, progressive disease will be reported as a SAE (see Section 8.2.2) and will also be documented on an AE eCRF. All observed or volunteered AEs, regardless of treatment group or suspected causal relationship to study drug, will be recorded on the AE eCRF.

Clinically significant changes in physical examination findings and new abnormal objective test findings (i.e. laboratory, x-ray, ECG) should also be recorded as AEs. The criteria for determining whether an abnormal objective test finding should be reported as an AE are as follows:

- associated with accompanying symptoms,
- requires additional diagnostic testing or medical/surgical intervention,
- leads to discontinuation from the study,
- requires additional concomitant drug treatment or other therapy, or
- considered clinically significant by the Investigator or Sponsor.

Any abnormality on blood testing should be confirmed by a repeat test.

The sign or symptom should be recorded as an AE, not as the objective test finding. (Correct: Hypokalemia. Incorrect: potassium of 3.3 mEq/L)

Minor abnormalities in laboratory tests compared to baseline, and repeat of these tests in the absence of any of the above conditions, do not meet the criteria for reporting as an AE. An abnormal test result that is later determined to be an error does not require reporting as an AE, even if it did meet one or more of the above conditions.

For all AEs, the Investigator must pursue and obtain information adequate to determine the causality (i.e. study drug or other cause) and outcome of the event and to assess whether it meets the criteria for classification as a SAE (see **Section 7.1.2**). Follow-up of the event is required until the event or its sequelae resolve or stabilize at a level acceptable to the Investigator and the study Sponsor/monitor.

There are no anticipated severe AEs associated with the administration of the investigational product, which will be given as a one dose infusion. Clinical experience with the parent antibody, CC49, used in larger doses and in radioimmunotherapy studies, demonstrated hematologic dose-limiting toxicities, but they were most likely due to the radiation dose to red marrow from radioimmunotherapy treatment [19, 40].

6.2 Biodistribution Measurements

Biodistribution assessments include qualitative analysis of distribution of ¹²⁴I-PEG-AVP0458 within the blood pool, normal organ distribution, and tumour uptake. PET/CT whole body imaging (see PET Imaging Charter) will be performed at the following 5 time-points upon administration of 124I-PEG-AVP0458: Day 0 (approximately 1 hour after infusion), day 1, day 2 or 3, day 4 or 5, and day 6 or 7.

Quantitative analysis will be performed by regions of interest defined for whole body, normal organs and tumour at each of the imaging time points. The individual PET/CT scans will be analysed to derive the concentration of ¹²⁴I-PEG-AVP0458 in the tumours per gram of tissue. The OLINDA program will be used for all dosimetry evaluations.

Qualitative PET/CT image and dosimetric analysis will be performed by the Austin PET Centre using the PET/CT images obtained at each study site.

6.3 Pharmacokinetic Measurements

PK analyses have the goal of defining C_{max} , AUC, C_L , and $T_{1/2}$. Levels of PEG-AVP0458 in the serum will also be evaluated. Descriptive statistics of serum concentrations and pharmacokinetic parameters will be calculated.

Standard PK analyses will be performed on 124 I-PEG-AVP0458 serum radioactivity data and serum concentrations of PEG-AVP0458 as measured in ELISA. Serum concentrations will be plotted graphically vs. time for all patients. PK analyses will be performed to estimate the maximal plasma concentrations (C_{max}), area under the curve (AUC), total serum clearance (C_{l}), and $T_{1/2}$. At the time points indicated in the Schedule of Events, blood serum samples (10 mL peripheral blood) will be obtained for PK of both administered radioactivity and PEG-AVP0458 protein. On Day 0, blood samples should be obtained prior to infusion, at completion of infusion, and at 1, 2 and 4 hours following completion of infusion.

Radioactive counting of serum samples will be performed in laboratories of the Ludwig Institute of Cancer Research. Results will be analysed and expressed as % injected dose per litre (%ID/L) and μ g/mL.

The concentration of PEG-AVP0458 will be measured in the peripheral blood by RDDT Laboratories using a validated ELISA assay method.

6.4 Immunogenicity

Human Anti-Diabody Antibody (HADA) levels will be measured in serum by ELISA to monitor the immunogenicity associated with the diabody. Time points for collecting the bloods for assays are listed in the Schedule of Events.

Immunogenicity (HADA titres) will be analysed with the goal of determining whether PEG-AVP0458 triggers any immune reaction against it and how much of an immunologic response is potentially associated with AEs.

